7.1 Study Subjects

7.1.1 Disposition of Subjects

The number of subjects enrolled in the study will be presented by training period and study period. The reasons for discontinuing prior to study completion will be summarized.

7.1.2 Clinical Investigation Plan (CIP) Deviations

All protocol deviations will be presented in the listings.

CIP330 Statistical Analysis Plan		Form
Revision [3.0] Page 12 of 25		Medtronic

7.1.3 Analysis Sets

All enrolled subjects who have at least one paired sensor and YSI[™]* measurement will be included in the efficacy analysis population. All enrolled subjects who have a sensor inserted will be included in the safety analysis population. Others who don't have sensors inserted will also be included in the safety analysis population.

7.2 General Methodology

All data collected from the time of screening until the end of the study will be collected either on eCRFs, subject survey or electronically by downloading the various devices and used as source data for analysis. Data and analysis will be summarized in a Clinical Study Report. Any deviations from original statistical plan and the rationale will be described in the Clinical Study Report.

Two study reports will be generated: one study report including data from US and all analyses except National Medical Products administration (NMPA) CGM for DS5; another study report including data from US and China and all analyses.

China only: The Clinical Study Report will be compliant with the elements from the NMPA 2016 No. 58 Announcement Annex 5 "Template of Clinical Trial Report of Medical Devices". There are no criteria and/ reasons for trial termination based on statistics.

7.3 Center Pooling

For each report, the relevant data will be pooled for analysis.

7.4 Handling of Missing, Unused, and Spurious Data and Dropouts

Data entry error or non-reasonable values will be resolved before data analysis. No imputations will be done for missing data.

7.5 Adjustments for Multiple Comparisons

Secondary endpoints will be evaluated in a fixed sequence of testing for adjustment of multiplicity.

7.6 Demographic and Other Baseline Characteristics

Subject characteristics, including age, gender, race, ethnicity, medical diagnosis (includes duration of diabetes diagnosis and type of diabetes), height, weight, BMI, CGM experience, pump experience, baseline HbA1c, and TDD will be summarized by descriptive statistics (mean, standard deviation, minimum, median, and maximum) for continuous variables and by counts and percentages for categorical variables.

7.7 Treatment Characteristics

The number of sensor insertions and sensor removals for every subject enrolled in the study will be presented.

A descriptive analysis of sensor disposition including sensor dislodgement and reasons why it dislodged will be included in the Final Report. Sensor insertion and removals will be characterized by the following:

- Sensor location
- Duration of sensor wear by investigational center subject report
- The number and percentage of sensors remaining in place at study end.
- Duration of sensor wear (subject report) by insertion site.
- Reason for removal: e.g., scheduled removal, adverse event, fell out.

The functional life of the sensor will also be characterized. The duration of sensor performance from the time of first valid Interstitial Signal (ISIG) to the last glucose reading (i.e., time to end of sensor life) will be described with Kaplan-Meier curves.

7.8 Interim Analyses

Not applicable.

7.9 Evaluation of Objectives

All datasets are categorized into primary datasets and secondary datasets for endpoints.

Primary datasets will be evaluated for

- Primary endpoints
- Secondary endpoints
- Agreement, ARD, Bias (Accuracy Analyses)
- Descriptive endpoints

Secondary datasets will be evaluated for

- Primary endpoints
- Secondary endpoints
- Agreement, ARD, Bias (Accuracy Analyses)

Datasets are described below:

Primary Datasets

Athena Plus algorithm

- Dataset 1: Adult (18 80 years), arm insertion location and 0 Calibration
- Dataset 2: Peds (2 to 17 years), buttock insertion location and 0 Calibration
- Dataset 3: Peds (2 to 17 years), arm insertion location and 0 Calibration

Medtronic

Secondary Datasets

Athena algorithm

- Dataset 4: Adult (18 80 years), arm insertion location and 0 Calibration
- Dataset 5: Adult (18 80 years), arm insertion location and two Calibrations (first calibration at 2 hours after insertion and second calibration at 8 hours after first calibration)
- Dataset 6: Peds (2 to 17 years), buttock insertion location and 0 Calibration
- Dataset 7: Peds (2 to 17 years), buttock insertion location and two Calibrations (first calibration at 2 hours after insertion and second calibration at 8 hours after first calibration)
- Dataset 8: Peds (2 to 17 years), arm insertion location and 0 Calibration
- Dataset 9: Peds (2 to 17 years), arm insertion location and two Calibrations (first calibration at 2 hours after insertion and second calibration at 8 hours after first calibration)

Athena Plus algorithm

- Dataset 10: Adult (18 80 years), arm insertion location and two Calibrations (first calibration at 2 hours after insertion and second calibration at 8 hours after first calibration)
- Dataset 11: Adult (18 80 years), arm insertion location and three Calibrations (first calibration at 2 hours after insertion, second calibration at 8 hours after first calibration, and 14 hours after second calibration)
- Dataset 12: Adult (18 80 years), arm insertion location and daily Calibrations (first calibration at 2 hours after insertion, second calibration at 8 hours after first calibration, 14 hours after second calibration and 24 hours after the previous calibration until end of wear)
- Dataset 13: Peds (2 to 17 years), buttock insertion location and two Calibrations (first calibration at 2 hours after insertion and second calibration at 8 hours after first calibration)
- Dataset 14: Peds (2 to 17 years), buttock insertion location and three Calibrations (first calibration at 2 hours after insertion, second calibration at 8 hours after first calibration, and 14 hours after second calibration
- Dataset 15: Peds (2 to 17 years), buttock insertion location and daily Calibrations (first calibration at 2 hours after insertion, second calibration at 8 hours after first calibration, 14 hours after second calibration and 24 hours after the previous calibration until end of wear)
- Dataset 16: Peds (2 to 17 years), arm insertion location and two Calibrations (first calibration at 2 hours after insertion and second calibration at 8 hours after first calibration)

CIP330 Statistical Analysis Plan		Form
Revision [3.0]	Page 15 of 25	Medtronic

- Dataset 17: Peds (2 to 17 years), arm insertion location and three Calibrations (first calibration at 2 hours after insertion, second calibration at 8 hours after first calibration, and 14 hours after second calibration)
- Dataset 18: Peds (2 to 17 years), arm insertion location and daily Calibrations (first calibration at 2 hours after insertion, second calibration at 8 hours after first calibration, 14 hours after second calibration and 24 hours after the previous calibration until end of wear)

Datasets (NMPA CGM for DS5 only) are described below:

Primary Datasets

Athena Plus algorithm

- Dataset 1: Arm insertion location and 0 Calibration
- Dataset 2: Buttock insertion location and 0 Calibration

Secondary Datasets

Athena algorithm

- Dataset 3: Arm insertion location and 0 Calibration
- Dataset 4: Arm insertion location and two Calibrations (first calibration at 2 hours after insertion and second calibration at 8 hours after first calibration)
- Dataset 5: Buttock insertion location and 0 Calibration
- Dataset 6: Buttock insertion location and two Calibrations (first calibration at 2 hours after insertion and second calibration at 8 hours after first calibration)

Athena Plus algorithm

- Dataset 7: Arm insertion location and two Calibrations (first calibration at 2 hours after insertion and second calibration at 8 hours after first calibration)
- Dataset 8: Arm insertion location and three Calibrations (first calibration at 2 hours after insertion, second calibration at 8 hours after first calibration, and 14 hours after second calibration)
- Dataset 9: Arm insertion location and daily Calibrations (first calibration at 2 hours after insertion, second calibration at 8 hours after first calibration, 14 hours after second calibration and 24 hours after the previous calibration until end of wear)
- Dataset 10: Buttock insertion location and two Calibrations (first calibration at 2 hours after insertion and second calibration at 8 hours after first calibration)

CIP330 Statistical Analysis Plan	Form
Revision [3.0] Page 16 of 25	Medtronic

- Dataset 11: Buttock insertion location and three Calibrations (first calibration at 2 hours after insertion, second calibration at 8 hours after first calibration, and 14 hours after second calibration)
- Dataset 12: Buttock insertion location and daily Calibrations (first calibration at 2 hours after insertion, second calibration at 8 hours after first calibration, 14 hours after second calibration and 24 hours after the previous calibration until end of wear)

7.9.1 Endpoints

7.9.1.1 Primary Endpoints

Sensor values will be compared to YSI[™] plasma glucose values during YSI[™] FSTs. A within 20% mean agreement rate (±20 mg/dL [1.1 mmol/L] when SG less than (<) 80 mg/dL [4.4 mmol/L]), μ , between sensor values and YSI[™] plasma glucose values during YSI[™] FST days will be evaluated against the null Hypothesis:

H0: $\mu \le 75\%$ H1: $\mu > 75\%$

Statistical Testing:

A generalized estimating equation (GEE) method model will be used. The one sided 95% lower confidence limit of the mean agreement rate will be tested against the threshold of 75%. For the GEE model, Exchangeable (exch) or Auto-regressive (AR1) or Independence (IND) correlation structure will be used, based on quasi-AIC (QIC).

Site effect will be evaluated. If it is not significant (p-value greater than (>) 0.1), site will not be included in the model. Sites with less than 6 subjects will be pooled into 'pseudo-sites' of at least 10 subject per pseudo-site. Pseudo-sites will be pooled by ranking those sites with less than 6 subjects by site number and pooling those sites in order of site number until the number of subjects reaches at least 10.

The primary endpoint will be independently evaluated for each of the 3 primary and 15 secondary datasets.

Pass/Fail Criteria:

The study pass/fail criteria is based on statistical hypothesis of the primary endpoints per dataset. The study will be considered as success when the evaluation criteria meets the predefined threshold.

Justification for Exclusion of Particular Information from the testing of the Hypothesis: Not Applicable.

CIP330 Statistical Analysis Plan		Form
Revision [3.0]	Page 17 of 25	Medtronic

Secondary endpoints will be evaluated only if the primary endpoint meets the predefined threshold.

7.9.1.2 Secondary Endpoints

7.9.1.2.1 National Medical Products Administration (NMPA) CGM for DS5

The four secondary endpoints will be evaluated in a fixed sequence of testing for adjustment of multiplicity. The results will be compared to the NMPA CGM criteria for sensor accuracy (SG limit of 50-400 mg/dL [2.8-22.2 mmol/L]):

 Sensor values from primary sensor will be compared to YSI[™]* plasma glucose values during YSI[™]* FSTs. A within 20% agreement rate (±20 mg/dL [1.1 mmol/L] when Reference BG less than or equal to (≤) 80 mg/dL [4.4 mmol/L]) between sensor values and YSI[™]* plasma glucose values during YSI[™]* FST days defined as p will be evaluated against the null Hypothesis:

H0: p ≤ 60%

H1: p > 60%

 Sensor values from primary sensor will be compared to YSI™* plasma glucose values during YSI™* FSTs. A mean rate in Zone A+B of Consensus Error Grid between sensor values and YSI™* plasma glucose values during YSI™* FST days defined as p will be evaluated against the null Hypothesis:

H0: p ≤ 90%

H1: p > 90%

 Sensor values from primary sensor will be compared to YSI[™]* plasma glucose values during YSI[™]* FSTs. A mean rate in Zone A+B of Clarke Error Grid between sensor values and YSI[™]* plasma glucose values during YSI[™]* FST days defined as p will be evaluated against the null Hypothesis.

H0: p ≤ 90%

H1: p > 90%

 Sensor values from primary sensor will be compared to YSI[™]* plasma glucose values during YSI[™]* FSTs. A mean absolute relative difference (MARD) between sensor values and YSI[™]* plasma glucose values during YSI[™]* FST days defined as μ will be evaluated against the null Hypothesis.

H0: *µ* ≥ 20%

Revision [3.0]

Medtronic

H1: *μ* < 20%

• Statistical testing

One proportion Z test will be used to obtain 97.5% lower confidence limit of the agreement rate, the mean rate in Zone A+B of Consensus Error Grid, and the mean rate in Zone A+B of Clarke Error Grid, which will be tested against corresponding threshold, respectively.

One sample T test will be used to obtain the 97.5% upper confidence limit of the MARD, which will be tested against corresponding threshold.

The secondary endpoints will be independently evaluated for each of the 2 primary and 10 secondary datasets (NMPA CGM for DS5 only).

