#### **10.2.1.6.4.1** Blood Glucose Monitoring During the YSI™\* FST

The frequency of blood draws for YSI™\* FST sampling is dependent on the average value of YSI-B and YSI-W probes of the previous sample, according to the following ranges:

- less than (<) 75 mg/dL (4.2 mmol/L); every 5 minutes (window of 3-8 minutes)
- greater than or equal to (≥) 75 mg/dL (4.2 mmol/L); every 15 minutes (window of 7-23 minutes)

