#### 25.8. General Considerations for Data Analysis

#### 25.8.1. Datasets Expected

The following datasets will be generated by the combination of:

- Primary sensors: For subjects 18 years and older and wearing 2 sensors, primary sensor will be
  assigned to the sensor with lower serial number in the same location. For subjects 7-17 years old
  and wearing 3 sensors, one primary sensor will be assigned to the sensor with lower serial
  number in the same location. The other primary sensor will be assigned to the sensor in the
  other location. For subjects 2 to 6 years old and wearing 2 sensors in the different locations, both
  sensors will be considered primary sensors.
- Secondary sensor: For subjects 18 years and older and wearing 2 sensors, secondary sensor will be assigned to the sensor with higher serial number in the same location. For subjects 7-17 years old and wearing 3 sensors, one secondary sensor will be assigned to the sensor with higher serial number in the same location.
- Athena Algorithm
  - o 0 Calibration
  - Two Calibrations (first calibration at 2 hours after insertion and second calibration at 8 hours after first calibration)
- Athena Plus Algorithm
  - 0 Calibration
  - Two Calibrations (first calibration at 2 hours after insertion and second calibration at 8 hours after first calibration)
  - Three Calibrations (first calibration at 2 hours after insertion, second calibration at 8 hours after first calibration, and 14 hours after second calibration)
  - Daily Calibrations (first calibration at 2 hours after insertion, second calibration at 8 hours after first calibration, 14 hours after second calibration and 24 hours after the previous calibration until end of wear)
- Age

10976639DOC Version D Page 138 of 170

Medtronic

- Adult (18 80 years)
- Pediatrics and adolescent (2 17 years)

For NMPA CGM analysis, all subjects (2 – 80 years) will be analyzed together.

- Location
  - Buttock
  - o Arm

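### The four NMPA accuracy tests use a one-proportion Z test and a one-sample T test with no stated unit and no allowance for about 48 to 160 repeated readings per sensor; the Z-test limits are wrong whichever unit is used

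*SAP*

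**What the plan says.** SAP 7.9.1.2.1 lists four NMPA endpoints, tested in fixed order: the 20% / 20 mg/dL agreement rate (against 60%), zone A+B of the Consensus grid (90%), zone A+B of the Clarke grid (90%) and MARD (20%). For the three rates, "One proportion Z test will be used to obtain 97.5% lower confidence limit of the agreement rate". For the fourth, "One sample T test will be used to obtain the 97.5% upper confidence limit of the MARD". The Synopsis and sections 5.2.2.1 and 25.9.2.1 of the protocol repeat this. Neither document says whether n counts paired readings or subjects. The wording for the second endpoint, "A mean rate in Zone A+B of Consensus Error Grid between sensor values", does not settle it.

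For the primary endpoint, a similar agreement rate from the same sessions, SAP 7.9.1.1 takes repeated readings into account: "A generalized estimating equation (GEE) method model will be used", with a choice of working correlation. SAP 7.9.1.4.6 keeps the sensor–YSI correlation descriptive because it ignores dependence.

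**The concern.** Readings from one sensor in one subject are not independent, and the sentence quoted for the rates permits two different calculations. If n counts pairs, the binomial standard error treats each subject's long series as independent observations, and the limit is too favourable. If n counts subjects, p(1−p)/n is the variance of a yes/no outcome per subject. A per-subject rate averaged over many readings varies far less, so the limit is too unfavourable. The Z limit is right only at an intraclass correlation (ICC) of 0 in the first case and 1 in the second. The T test for MARD is sound if run on per-subject values, but the plan does not say so.

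At stake are the limits compared with the NMPA criteria in the US and China report. Because testing is in fixed sequence, a false failure on the Consensus grid would also block the Clarke and MARD tests.

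**Working it through.** **The plan's own figure.** No power or sample size is stated for the NMPA endpoints. The only power claim (over 80% with 100 subjects, SAP 6.1) concerns the primary endpoint, and its simulation inputs are not given, so there is nothing to reproduce here.

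**Readings per sensor.** At or above 75 mg/dL the YSI is drawn "every 15 minutes (window of 7-23 minutes"); below that, every 5 minutes (protocol 10.2.1.6.4.1).
- Ages 14–80: 4 sessions × 8 h × 4 per hour = 128. Two hypoglycemic challenges of about 2 h at 5-minute sampling add 2 × 2 × (12 − 4) = 32, giving 160.
- Ages 7–13: 2 × 6 × 4 = 48.
- Ages 2–6: fingerstick reference only, so no YSI pairs.

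**Subjects.** Protocol 25.8.1 pools ages: "For NMPA CGM analysis, all subjects" are taken together. It gives one primary sensor per subject per location, so subject and sensor clusters coincide unless a sensor is replaced. Planned completers are 140 adults and 120 aged 2–17. Assume 40 in each of ages 2–6, 7–13 and 14–17, and use the lower count of 128.
- Arm: 180 × 128 + 40 × 48 = 24,960 pairs from 220 subjects.
- Buttock: 40 × 128 + 40 × 48 = 7,040 pairs from 80 subjects.

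**Pair as unit.** Effective cluster size Σm²/Σm is 121.8 (arm) and 106.2 (buttock). Design effect DEFF = 1 + (effective size − 1) × ICC. Half-width = 1.96 × √(0.9 × 0.1 × DEFF / pairs). The naive value has DEFF = 1: 0.37 points (arm) and 0.70 (buttock). Errors are one-sided at a true 90% (nominal 2.5%), from beta-binomial simulation with 10,000 runs per cell.

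| ICC (assumed) | DEFF arm / buttock | Correct half-width, points, arm / buttock | Simulated error of pair-level Z, arm / buttock |
|---|---|---|---|
| 0.02 | 3.4 / 3.1 | 0.69 / 1.23 | 14.9% / 14.0% |
| 0.05 | 7.0 / 6.3 | 0.99 / 1.75 | 23.3% / 22.6% |
| 0.10 | 13.1 / 11.5 | 1.35 / 2.38 | 30.4% / 29.2% |
| 0.20 | 25.2 / 22.0 | 1.87 / 3.29 | 35.1% / 36.3% |

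With the variance taken at 90%, naive and clustered tests disagree only if the observed rate lies between about 90.4% and 90.7–91.9% (arm), or 90.7% and 91.2–93.3% (buttock).

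**Subject as unit.** The half-width at 90% is 1.96 × √(0.09/220) = 3.96 points (arm) and 1.96 × √(0.09/80) = 6.57 (buttock). The correct variance of a subject's rate is p(1−p)[ICC + (1−ICC)/m], which gives 0.69–1.81 and 1.21–3.02. For power, the limit uses the observed rate, so the pass marks are 93.3% (arm) and 94.8% (buttock). With a true 93% and ICC 0.10, simulated power is 31% (arm) and 2% (buttock), against 99.8% and 83% for a T test on subject rates.

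**The two readings compared.** For the same data the naive half-widths differ by √(24,960/220) ≈ 10.7 times (arm) and √(7,040/80) ≈ 9.4 times (buttock).

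**MARD with pairs as unit.** Assume a standard deviation of absolute relative difference of 10–15 points. The naive half-width of 0.12–0.19 should be 0.23–0.93 (arm), and 0.23–0.35 should be 0.41–1.64 (buttock).

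**Shielding of the 60% test.** SAP 7.9.1.1 says "Secondary endpoints will be evaluated only if the primary endpoint meets the predefined threshold". At a true 60%, passing the 75% primary test needs an observed rate about 7 to 23 standard errors too high. The two agreement rules differ slightly below 80 mg/dL, but the 60% test is well protected.

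**The case against.** A one-proportion Z test needs a binary outcome. Agreement and zone membership are binary for a pair, and the descriptive error-grid analysis in SAP 7.9.1.4.3 counts pairs. The phrase about a mean rate proves little, since the primary endpoint uses similar words for a GEE on repeated readings. The pair is therefore the natural unit, and this stands. It does not rescue the plan, because that reading gives limits that are too narrow. The subject-unit figures matter only if the analyst reads the sentence the other way, where the harm is lost power rather than a false claim.

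The ICC, pediatric split and ARD standard deviation are assumptions, and the 14–36% error applies only at a true rate of exactly 90%. Both points stand, but the direction does not depend on them. At ICC 0.01 the analytic error is already 5–11% for 48 to 160 readings. A second simulation with 120 buttock and 260 arm subjects, 48–160 readings each and ICC up to 0.30 gave 15–40% at the 90% threshold.

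A T test on per-subject values is a simpler remedy. It is workable, with 2.5–4.9% error at 90% in that second simulation, but it is no better controlled than logit-scale robust limits and gives each subject equal weight instead of each reading.

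**Conclusion.** The concern holds and should be fixed. As written, the Z-test limits for three NMPA endpoints are wrong under either unit: about 1.8 to 5.0 times too narrow if pairs are counted, and about 2.2 to 5.8 times too wide if subjects are. The MARD limit is sound only if the T test is run on per-subject values. The multipliers rest on an assumed ICC of 0.02–0.20 and the assumed age split; the defect itself does not.

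The consequences are bounded. The 60% test is shielded by the primary gate, and the 90% and MARD tests change conclusion only near threshold. Study success rests on the primary endpoint, and the US-only report leaves these tests out: "one study report including data from US and all analyses except National Medical Products administration (NMPA) CGM for DS5". The US and China report would still carry incorrect limits.

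**What to change.** Replace the Z and T tests in SAP 7.9.1.2.1 with a GEE like that of the primary endpoint: logit link for the three rates and identity link for MARD. Name the paired reading as the observation and the subject as the cluster, specify a robust standard error with a small-sample correction, and take the one-sided 97.5% limits from that model, on the logit scale for the rates. A subject-level bootstrap is an alternative.

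In the simulation at 90%, logit-scale cluster-robust limits gave 2.4–3.8% one-sided error and identity-scale limits 2.9–6.2%, so the logit scale should be specified.

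The cost is one paragraph in the SAP and its three copies in the protocol (Synopsis, 5.2.2.1, 25.9.2.1). If the sponsor classes the protocol change as significant, section 27.10 requires submission to the IRB/EC and, where applicable, the regulator. The limits will be wider and less favourable than a pair-level Z test would report.
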